**Figure 5. Aim 2 PD and PDT Mediation Mechanisms**

**Data Analysis Plan for Aims 3.** For moderation model testing, we will apply similar approaches as in Aim 1 and add the moderator and moderator-by-intervention interaction terms in the analysis. Figure 6 below describes the model to be tested under Aim 3. For models with a significant moderator-by-intervention term on teacher effectiveness outcomes, we will then further test mediation-moderation mechanisms by expending the mediation model described above. These methods have been utilized in our previous studies.

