Phase	Phase II/III
Objectives	This study include three specific aims: Aim 1. To evaluate the short- and longer-term effectiveness of, PD alone ( PD ), PD + T-Wellness ( PDT ), and control (C, provision of child mental health and referral information). Hypotheses: (a) PD is more effective than control; and (b) PD with T-Wellness ( PDT ) is more effective for CHWs/teachers than PD alone; and (c) PDT has a more favorable cost-effectiveness ratio than PD alone; Aim 2. To examine effectiveness mechanisms and theory of change underlying the EBIs. Hypotheses: the mediational mechanisms of PD (teacher EBI strategy use as a mediator between intervention and child outcomes) and PDT (teacher stress management and EBI strategy use as mediators) will be supported; Aim 3. To examine implementation contextual factors and mechanisms that contribute to CHWs' (teachers') uptake and sustainment of EBI strategies within PD and PDT schools. Hypotheses: better fidelity, teacher mental health and more supportive contexts will be associated with better teacher uptake and sustainment of EBI strategies and more effective task-shifting.

Methodology	A cluster randomized controlled trial (cRCT), single blind and mixed-methods design will be applied. All study activities will be conducted in Uganda. Thirty-six public primary schools (18 urban and 18 rural), 540 teachers (~15 per school) and 1,980 parent-child pairs (~55 per school) will be recruited. Schools will be assigned to one of three conditions (PD, PDT, control). A stratified-block randomization procedure will be applied to ensure approximately similar characteristics across study regions and conditions.
Endpoint	Effectiveness outcomes will be assess 3 times (Time 1= before intervention; Time 2= immediate after PD/PDT intervention; Time 3= 12 months after Time 2). The primary teacher effectiveness outcomes (or intermediate effectiveness outcomes) are teachers' EBI strategy use and teacher stress management. The primary child effectiveness outcomes are child externalizing and internalizing problems (mental health outcomes). The secondary child effectiveness outcomes are emotion regulation, executive functioning (ability for cognitive processes that are foundation for the cognitive control of behavior), and social relationship (student-teacher relationship, peer relationship).

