Population	The study populations include: (1) Teachers for the T-Wellness User-centered & Optimization testing (n=60; from 4 non-RCT schools in year 1); (2) Intervention implementers (n=8; 6 TTC trainers and 2 mental health professionals from urban/Kampala and rural/Hoima regions; (3) Primary school teachers/head teachers (n=540) from 36 schools and PTA leaders (n=24) from 24 intervention schools; and (4) Children and caregivers (n= 1980 parent-child pairs) from 36 study schools.
Study Sites	36 schools (12 receiving PD, 12 receive PDT, and 12 control).
Number of participants	2544 adults and 1980 children for Aims 1-3 (This is not including 60 teachers for the T-Wellness User-centered testing during Year 1 preparation year).

[figure not shown]

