Contextual Moderators (Pre/T1 and Post PD training, and during PD implementation)	a) Outer setting: Urban/rural region (Primary moderator) b) Fidelity: 4 PD/PDT measures (F, T) c) Inner setting: School EBI climate (e.g., work environment, team work alliance, leadership) (T); d) Individual/Teacher characteristics (e.g., EBI readiness/attitude; wellness) (T) e) Intervention characteristics: Acceptability; Appropriateness (T) f) Processes: Partnership Quality (e.g., TTC and teacher/PTA partnership) (T)	b) 4 Fidelity measures  (1) Adherence (F) (deliver the core content): PD/PDT Fidelity Checklists (completed after each training day & coaching session) (2) Quality of implementation (T) (Teacher Satisfaction (T) (post PD training and T2) ( $\alpha=.72$ )  and ratings of Coaches' competence); (3) Engagement (T) Strategy Knowledge  (T) (EBI knowledge gain before-after training) (test-retest $r=.35-.43$ )  ; (4) Exposure (F): Attendance tracking  ; C) School Environment Survey  ; Organization Climate Questionnaire ( $\alpha=.65-.85$ )  d) Teacher demographic  ; PHQ-mental health  ; EBP Attitude Scale  ; e) Applied Mental Health Research Dissemination and Implementation Measurements (AMHRG)  ; f) Partnership Questionnaire 
Demo (T1)	Family/Student Demo (e.g., parenting, well-being) (P)	Family: Demo  ; Parent EBI Practices (P) ( $\alpha=.69-.80$ )  ; PHQ ( $\alpha=.90$ ) 
PD/PDT Cost	Program implementation costs;	Implementation costs: actual program costs (with & without monitoring cost) 

**Note.** For **child effectiveness outcomes**, primary data source is parent-report (P); and secondary data source is child-report/testing (C). For **teacher effectiveness outcomes**, primary data sources is classroom observation (O) & teacher report (T); and secondary data source is Parent (P) report. **CFIR contextual data** will be gathered from Training/coaching session tracking data from facilitator report (F) and teachers-report (T). **Suicidal behaviors** are NOT included because this study focuses on preventive intervention and young children (ages 4-10 years). The measures used in young children usually do not include suicidal items. However, parent, teacher, and child reported depressive symptoms will be included.

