## 9 Statistical Considerations

**Data Analysis Plan for Aim 1.** Prior to any outcome analyses, we will generate summary statistics for all data, summarizing with means and standard deviations for continuous variables and frequencies for categorical variables. The distribution of study variables and missing data patterns will be inspected. To estimate effectiveness, we will apply intention-to-treat (ITT) analyses and first focus on between-subject comparisons of intervention vs. control (comparing *PD* to control, comparing *PDT* to control, and comparing *PD* to *PDT*). We will estimate the impact of *PD* on children and teachers post-intervention (T2, 4-5 months after T1) and at one-year follow up (T3, 18 months after T1, or 12 months after T2). **Figure 4** below describe the model to be tested under Aim 1. School and class nesting will be considered, and a multiple imputation strategy will be applied to account for missing data. Linear mixed effect models, using SAS PROC MIXED, will be applied to examine short and longer-term impacts. We will first examine the immediate impact by modeling post-intervention outcomes (T2) as a function of intervention, adjusting for T1 outcome measures. The model accounts for between-subject (within-school and -class) correlation by including school- and classroom-level (when appropriate) random intercepts. The outcomes will be modeled as:  $Y_{ij} = \beta_1 I_j + \beta_2 C + \beta_3 X_{ij} + \gamma_j + \gamma_k + \epsilon_{ijk}$ , where  $Y_{ij}$  is the outcome for the student  $i$  in school  $j$ .  $I_j$  is intervention status (a categorical variable, with 3 levels) for school  $j$ , representing two dummy variables (control as the reference).  $C$  is the cohort indicator for

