school, where  $C=1$  if is in the second cohort, 0 for the 1st cohort.  $X_{ij}$  is the baseline value of the outcome for student  $i$  in school  $j$ . In the models,  $\beta_1$  represents the intervention impact,  $\beta_2$  is the effect of the second cohort,  $\beta_3$  is the effect of baseline measure,  $\gamma_j$  is the school-level random effect and  $\gamma_k$  is the class-level random effect (when appropriate), and  $\epsilon_{ijk}$  is the error term for student  $i$  in school  $j$  and  $k$  class. Next, we will study longer-term effectiveness outcomes (T2 to T3) by applying growth curve models and using repeated assessments over time. In these growth models, we will add time-relevant parameters to the model above, including school-level random slopes. The post-baseline scores will be modeled as a linear function of time/slopes, intervention indicator, and intervention-by-time interactions, adjusting for T1 scores and cohort. The long-term outcome will be modeled as:  $Y_{ij} = \beta_1 I_j + \beta_2 t + \beta_3 I_j * t + \beta_4 C + \beta_5 X_{ij} + \gamma_j + \gamma_k + \epsilon_{ijk}$ . A significant  $\beta_3$  would indicate the effect of the intervention depends on time; in this case, we will estimate the slopes for each condition, and the difference between the conditions with respect to the mean outcome scores. The analytical methods that we propose have been applied successfully in our previous US and LMIC studies. Cost-effectiveness analysis of *PD* and *PDT* implementation models will be examined using approaches that have been applied in previous school-based and parenting-based child mental health promotion research. The analysis will center on incremental cost-effectiveness ratios (ICERs), where the numerator represents the cost difference between the intervention arms and the control, and the denominator represents the difference in average intervention effects. To that end, the cost-effectiveness analysis of the intervention will involve examining how much the *PD/PDT* intervention costs to achieve a unit of effect relative to the control group. The effects of the intervention will be estimated using the effect sizes  $d$  (standardized mean difference between comparison groups) from an ITT approach. For the effectiveness outcomes, we will use an effect size of 0.2-0.4 as a benchmark; this corresponds to a small to medium effect size according to Cohen. We will calculate the ICERs and compute the per-participant cost per 0.2-0.4 SD change for each effectiveness outcome. Reporting of the analysis will follow the Consolidated Health Economic Evaluation Reporting Standards (CHEERS).

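### Aim 3 gives teacher-level moderators no school-level random slope, so their interaction tests reject too often if those slopes differ between schools

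*Combined protocol and SAP*

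**What the plan says.** Section 9, Data Analysis Plan for Aims 3, gives no equation. It says the analysis will "apply similar approaches as in Aim 1 and add the moderator and moderator-by-intervention interaction terms in the analysis", and it makes a significant interaction on a teacher outcome the condition for going on to mediation-moderation models.

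The random effects therefore come from the Aim 1 plan in the same section. The T2 model handles within-school and within-class "correlation by including school- and classroom-level (when appropriate) random intercepts". For T2 to T3, "we will add time-relevant parameters to the model above, including school-level random slopes", although the printed growth equation shows only the two intercept terms. SAS PROC MIXED is named. No degrees-of-freedom method, significance level or slope variance is stated.

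Table 2 lists moderators at different levels. The primary one is a school attribute: "Urban/rural region (Primary moderator". Others are measured on individual teachers: "d) Individual/Teacher characteristics (e.g., EBI readiness/attitude; wellness) (T".

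**The concern.** Arm varies between schools, while a teacher-level moderator varies mainly among the roughly 15 teachers inside a school. Their product is a cross-level interaction: it asks whether the average within-school slope of outcome on moderator differs between arms.

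With no random slope for the moderator, the model assumes one common slope for all schools of an arm. Suppose wellness matters more in some schools than in others for reasons unrelated to PD or PDT. Twelve schools' slopes are then being compared with twelve others, but the model computes the standard error as if every teacher gave independent information on the slope. The standard error is too small. The plan already guards against the same clustering error for intercepts and, in the growth model, for time.

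At stake are secondary statements about which teachers benefit, and one of the conditions for the mediation-moderation analysis.

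**Working it through.** **Inputs from the documents.** "36 schools (12 receiving PD, 12 receive PDT, and 12 control"; "540 teachers (~15 per school" (36 × 15 = 540, which agrees). The plan states no error rate, power or ICC for this test, so there is no design figure to reproduce.

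**Assumptions not in the documents.** Two-sided 5% test; residual SD 1 and moderator SD 1; outcome ICC 0.15; moderator ICC 0.10; no true interaction; slope SD t between schools from 0 to 0.30, in residual SDs per moderator SD.

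**Approximation.** With m = 15 teachers, the expected within-school moderator sum of squares is Sx = (m − 1)(1 − ICCx) = 14 × 0.90 = 12.6.

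- True variance, per school: t²(1 + 2/(m − 1)) + 1/Sx.
- Variance that the model without a moderator slope believes: (1 + t²(1 − ICCx))/Sx.
- Rejection rate: 2(1 − Φ(1.96/√ratio)), where ratio is true over believed. The number of schools cancels.

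At t = 0.20:

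- True: 0.04 × 1.1429 + 0.0794 = 0.1251.
- Believed: 1.036/12.6 = 0.0822.
- Ratio 1.521, square root 1.233, 1.96/1.233 = 1.589, rate 11.2%.

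**Simulation.** REML fits with 2,000 runs per setting (Monte Carlo standard error about 0.5 points at 5% and 0.7 at 12%), plus a second simulation built on within-school slope estimates. The last column adds a school random slope for the moderator and uses 36 − 3 = 33 degrees of freedom.

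| Slope SD | Approximation, 1 df | No moderator slope, 1 df | Second simulation, 1 df | No moderator slope, 2-df three-arm test | With moderator slope, 1 df |
|---|---|---|---|---|---|
| 0 | 5.0% | 4.2% | 4.7% | 4.6% | 3.2% |
| 0.10 | 6.6% | 5.8% | 6.8% | 6.8% | 4.2% |
| 0.15 | 8.5% | 8.2% | 8.2% | 9.8% | 4.4% |
| 0.20 | 11.2% | 11.6% | 11.1% | 14.0% | 4.6% |
| 0.30 | 17.9% | 18.8% | 17.2% | 25.5% | 4.8% |

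**Variations.**

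- PD against PDT only (24 schools): 4.2%, 5.8%, 10.8% and 18.4% at slope SD 0, 0.10, 0.20 and 0.30. With the moderator slope and 24 − 2 = 22 degrees of freedom: 2.6%, 3.4%, 5.0% and 5.0%.
- Ten teachers per school: 8.6% at 0.20 and 13.3% at 0.30.
- Moderator ICC from 0 to 0.20 (approximation): 11.9% to 10.5% at slope SD 0.20.

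**Do the growth model's random time slopes cure it?** No. With a school intercept, a school time slope and no correlation between a teacher's two measurements (800 runs), the 1-df test rejects at 5.1% with slope SD 0 and 16.6% at 0.20.

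**The case against.** **The model is partly inferred.** Aim 3 speaks of similar approaches, prints no random-effects structure, and refers to Figure 6, which was not available in the text I worked from. A reader might infer that the plan commits to random intercepts only. The documents do not support that, because the growth model names school-level slopes. What stands is narrower: those slopes are introduced as time terms, they do not help here, and no visible text gives the moderator one.

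**The inflation depends on an undocumented quantity.** A reader might take 10-20% as the expected error rate, or treat slope variation of that size as ordinary. Neither follows. For the 1-df test to reach that band with 15 teachers per school, the slope SD must be roughly 0.18 to 0.32; at 0.10 the excess is only a point or two. The plan's own theory, that school and implementation context shape effects (Section 1.2), makes some variation plausible but says nothing about its size. Nor should the chance that either PD or PDT shows an interaction be charged to this defect alone. Two uncorrected contrasts sharing a control already give about 9% with no slope variation.

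**The reach is limited.** This objection stands. Region is unaffected. The Aim 3 hypothesis is worded as association with uptake in PD and PDT schools. Fidelity to and satisfaction with PD/PDT have no control-arm values, so only PD against PDT applies to them. A false interaction does not by itself open the mediation path, because the Aim 2 plan admits only intermediate outcomes that improved significantly.

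**Conclusion.** The point holds in a limited form. For moderators that vary within schools, the visible Aim 3 plan does not let the slope differ between schools, and the interaction test is anti-conservative if it does. Under the assumptions listed, the 1-df error rate runs from nominal to just under 20% over slope SDs of 0 to 0.30. Where the trial would fall in that range cannot be judged from the documents. The primary effectiveness comparisons and purely school-level moderators are untouched. This is a cheap improvement to secondary analyses, not a threat to the main conclusions. It is still more than a missing detail, since the suggested model held its level at every slope SD examined.

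**What to change.** Add a sentence to the Aim 3 plan: for each moderator measured on individual teachers, the model includes a school-level random slope for that moderator alongside the school random intercept, and the interaction is tested on between-school, small-sample degrees of freedom. State the method. The checks above used 33 for three arms and 22 for PD against PDT, whatever the slope variance estimate. If the slope variance is estimated as zero, drop the slope; the model then reduces to the planned one. Models for region and other purely school-level moderators stay as they are.

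The cost is one extra RANDOM term in PROC MIXED, wider intervals for these interactions, a slightly conservative test when slopes do not vary (about 3% in the check), and occasional zero-variance or convergence notes.

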## 1.2 **Rationale**

This study involves efforts to advance the science of prevention in early childhood mental health in low-resource communities. We will investigate the effectiveness, practical implementation strategies, and underlying mechanisms of the *PD* in urban and rural Uganda. We will compare effectiveness of two *PD* implementation approaches (with and without T-Wellness) using a hybrid effectiveness-implementation CRCT. **Figure 3** shows the conceptual model for *PD* and *PDT* Theory of change in LMIC contexts, which considers *intermediate intervention effectiveness outcomes* (teacher EBI practice) and *distal effectiveness outcomes* (including primary child mental health outcomes and secondary child behavioral outcomes, defined in Table 2). *PD* is expected to change teachers' EBI practices; and the impact of *PD* on distal child mental health outcomes will be mediated primarily through changes in teachers' practice of EBI strategies. Similarly, we expect that *PDT (PD+T-Wellness)* will also have impact on distal child mental health outcomes, and this will be mediated primarily through improvement in both teachers' EBI practices/behaviors and teachers' stress management skills (cognitive and behavioral control/ coping of stress). We anticipate *changes in child behaviors will be observed in the secondary outcome domains before the mental health outcomes* (primary distal outcomes). Because *PD/PDT* will be implemented in diverse contexts, our theory of change also considers moderators from aspects of the Consolidated Framework for Implementation Research (CFIR), which proposes that five domains of contextual factors can impact effectiveness-implementation. Specifically, we expect that certain *individual, intervention implementation, and school contexts* may also influence (or moderate) intervention effectiveness. We consider geographic region (urban/ rural) as the primary moderator, and other CFIR factors listed in the figure as secondary moderators. This theory of change has been partially tested (constructs in 'red' in Figure 3) and supported in previous *PD* studies. This study will formally examine the cost-effectiveness and test the *PD/PTD* theory of change with a larger diverse sample and using scalable approaches. We select a foreign low-resource country as our study site because it provides an ideal setting to test how a mental health system can be strengthened through careful consideration of strategies while simultaneously examining effectiveness outcomes of an EBI. Also, Ugandan context is similar to other underserved and under-resourced communities in the US and other LMICs. Therefore, knowledge generated from our study will be relevant globally.

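### Aim 3 screens about 11 secondary moderators on at least two teacher outcomes with no stated error control, and significance alone decides which go on to moderated mediation

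*Combined protocol and SAP*

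**What the plan says.** Under the Aim 3 analysis plan in section 9, the team will work as in Aim 1 and "add the moderator and moderator-by-intervention interaction terms in the analysis". What happens next depends on significance: "For models with a significant moderator-by-intervention term on teacher effectiveness outcomes, we will then further test mediation-moderation mechanisms". No significance level or adjustment is attached to that word anywhere in section 9.

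Section 1.2 ranks the moderators: "We consider geographic region (urban/ rural) as the primary moderator, and other CFIR factors listed in the figure as secondary moderators". That figure is not reproduced in the text available, so the count has to come from Table 2 in section 6.1. Beyond region, Table 2 lists four fidelity measures, school climate (a school environment survey and an organization climate questionnaire), teacher characteristics (demographics, a PHQ and an attitude scale), acceptability and appropriateness of the intervention, and partnership quality.

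Section 2.1 names two primary teacher outcomes: use of the evidence-based strategies, and stress management. Table 2 measures them with several instruments and treats both observation and teacher report as primary sources. The Protocol Summary hypothesises for Aim 3 that "better fidelity, teacher mental health and more supportive contexts will be associated with better teacher uptake and sustainment of EBI strategies".

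**The concern.** A screen of many interactions, each judged on its own, will often turn up something when nothing is there. Here the screen also selects: a term that crosses the line is taken into a further model fitted to the same data, and nothing in the plan allows for how it was chosen. Naming region as the primary moderator does not settle this, because the carry-forward rule applies equally to every moderator.

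The consequence is practical. Section 6.1 presents this work as a basis for decisions about how to deploy the programme, and the protocol describes moderation itself as a mechanism. A chance interaction with, say, school climate could therefore be reported as an implementation mechanism and influence scale-up.

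**Working it through.** The plan states no error rate or power for Aim 3, so there is no figure to reproduce. The check computes what the stated rule implies.

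**Inputs**

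- Secondary moderators (Table 2): 4 fidelity + 2 climate scales + teacher PHQ + attitude scale + acceptability + appropriateness + partnership = 11. Scoring climate as one and acceptability with appropriateness as one gives 9. Adding demographics to the 11 gives 12, and splitting implementation quality into satisfaction and coach competence gives 13.
- Teacher outcomes (section 2.1): 2, as a minimum.
- Clusters (Protocol Summary): 36 schools, 12 per arm.
- Assumed, because not stated: two-sided 0.05 per test, no true moderation, one test per moderator and outcome, one time analysis.
- Correlation between test statistics: not given; shown for 0, 0.5 and 0.8.

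**Formulas**

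For m independent tests, P(at least one false interaction) = 1 − 0.95^m. For m normal test statistics with common correlation ρ,

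P = 1 − ∫ φ(u) [Φ((1.96 − √ρ·u)/√(1−ρ)) − Φ((−1.96 − √ρ·u)/√(1−ρ))]^m du.

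The expected number of false interactions is 0.05m at any correlation.

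**Number of tests**

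- Main count: 11 × 2 = 22.
- Upper count with both arm contrasts: seven moderators (four fidelity measures, acceptability, appropriateness, partnership) appear to have no control-arm values, so each allows only the PD-versus-PDT contrast. The other four (two climate scales, PHQ, attitude) allow two. That gives 7×1 + 4×2 = 15 per outcome, and 15 × 2 = 30.
- Lower count: one test for each of the five secondary domains, on two outcomes: 5 × 2 = 10.

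| Tests | ρ = 0 | ρ = 0.5 | ρ = 0.8 | Expected false |
|---|---|---|---|---|
| 10 | 0.40 | 0.29 | 0.17 | 0.5 |
| 22 | 0.68 | 0.44 | 0.23 | 1.1 |
| 30 | 0.79 | 0.51 | 0.26 | 1.5 |

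For 22 independent tests: 1 − 0.95^22 = 0.676. With 9 or 13 moderators (18 or 26 tests) the independent figures are 0.60 and 0.74. If the unstated level were 0.01, 22 independent tests would give 1 − 0.99^22 = 0.20.

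**Second stage**

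These figures take 22 independent tests, 11 per outcome. The chance of a false interaction on one outcome is 1 − 0.95^11 = 0.431. If the second stage requires both the interaction and the mediator-to-child path to be significant, and that path is detected with probability p, then P(false moderated mediation) = 1 − (1 − 0.431p)². This is 0.57 at p = 0.80, and 0.04 at p = 0.05 (no true path). Simulating a Sobel-type product test, the kind the Aim 2 plan describes, gives 0.18 when the path has 80% power.

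**With control**

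Bonferroni over 22 tests uses 0.05/22 = 0.00227 per test. The chance of any false interaction becomes 1 − (1 − 0.00227)^22 = 0.049 under independence, and is lower under positive correlation. Holm controls the same rate.

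**The case against.** The best defence is that the plan already ranks region above everything else, that secondary moderators in an implementation aim are commonly understood as exploratory, and that Aim 2 admits to mediation testing only intermediate outcomes that improved significantly. Part of this stands. If the Aim 2 condition carries into Aim 3, some significant interactions will go no further. But it asks whether the teacher outcome improved, not how many interactions were searched, and it would open if the programme works as expected. No section calls the secondary moderators exploratory.

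Four stronger readings are tempting and are not supported:

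- *A false mechanism is more likely than not.* At 22 tests this is true only at low correlation; at 0.5 the figure is 0.44.
- *Two arm contrasts for every moderator, hence 44 tests.* About seven moderators appear to exist only in intervention schools, and Aim 3 is framed within PD and PDT schools, so 30 is the ceiling for two outcomes and one time analysis.
- *The Aim 3 hypothesis makes every interaction a confirmatory claim.* It predicts that three broad areas are associated with uptake and sustainment. It does not predict interactions with intervention, and it does not name acceptability, appropriateness or partnership.
- *The screening rate is the rate of false moderated mediation.* The second stage must also pass, and the range above runs from 0.04 to 0.57 depending on the test and the mediator path.

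The count of 11 is also a reading of Table 2, not a number in the protocol, and the moderator list may be shorter in the figure that is not shown.

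**Conclusion.** The concern holds for the interaction screen. Followed as written, the Aim 3 rule has a chance of at least one false interaction well above 0.05: 0.44 for 22 tests at correlation 0.5 (0.23 to 0.68 for correlation 0.8 to 0), rising to 0.51 (0.26 to 0.79) at 30 tests. Even the 10-test count gives 0.17 to 0.40.

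This rests on an assumed two-sided 0.05, on no true moderation, on a moderator count taken from Table 2, and on reading the plan's silence as no adjustment. None of the correlations or counts considered brings the rate near 0.05 at that level. How often a false moderated-mediation result would follow is uncertain and may be well below the screening rate. This is an inexpensive improvement that changes which terms go forward and what Aim 3 can conclude; it does not affect the Aim 1 comparisons.

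**What to change.** Rewrite the Aim 3 paragraph of section 9 to say:

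1. The region-by-intervention interaction on observed evidence-based-strategy practice, with its contrast and time point named, is the single primary Aim 3 interaction test, at two-sided 0.05.
2. The secondary moderators are listed by name and scale and, across the named teacher outcomes, form one family with Benjamini-Hochberg control at 0.05 (or Holm), with one test per moderator and outcome. Use the joint 2-df interaction where the moderator is measured in all three arms, and the 1-df PD-versus-PDT interaction where it exists only in intervention schools (fidelity, acceptability, appropriateness, training partnership).
3. Only surviving terms support a moderation claim and enter the mediation-moderation model. All others are reported as estimates with intervals.
4. Secondary moderation, and any moderated mediation that follows from it, is labelled exploratory.
5. The plan states whether the Aim 2 requirement of significant improvement also applies here.

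The cost is a paragraph of text and no new data collection. The downside is that fewer secondary moderators will be called significant, when power for interactions with 36 schools is already limited.
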